The following baseline assessments will be completed prior to administration of study drug:

- Review of medical history
- Although the risk of serious side effects is low when diclofenac is applied to the skin, pregnant women will be excluded from this study. Urine pregnancy screening will be conducted for all female subjects of childbearing potential.* Women who have a positive pregnancy test would be excluded.
- Limited skin examination and blood pressure measurement. We will exclude patients with SBP > 160 and DBP > 95 at screening.
- Collect pain information such as onset, pain intensity 24 hours prior and immediately before study drug application

*Female subjects are considered "of child-bearing potential" if they (a) are anatomically and physiologically capable of becoming pregnant and (b) they will be, or could possibly be, engaging in sexual activity with males while study interventions that pose the possibility of harm to a fetus are occurring. Note that this time period also includes any time after study activities have ended where the protocol specifies the use of contraception.

Dose, Delivery and Dispensing

After obtaining consent, subjects will be randomized to one of two study groups (Bonipar or diclofenac topical solution 1.5%), utilizing a predetermined randomization schedule in a 1:1 ratio.

The study drug, Bonipar, is stored in an opaque plastic bottle so that the contents may be protected from both direct and indirect sunlight because it is likely that sunlight could result in the degradation and/or decomposition of some of the essential oils contained in Bonipar. For blinding purposes, Diclofenac topical solution 1.5% will be stored in the same opaque plastic bottle. The bottles will be labeled either "Drug A" or Drug B" according to their designation, lot #, BUD (beyond use dating), dosing instructions, and FDA statement "Caution: New Drug—Limited by Federal law to investigational use". Thus, the drugs would be blinded to both the patients and to the investigators. Only the unblinded Clinical Research Coordinator (CRC) will have access to the randomization scheme and will have the knowledge of the dispensed drugs. To avoid any bias, the principal investigator would strongly advise the study technicians not to communicate any information regarding the 2 drugs to their investigator colleagues.

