All subjects will be instructed on the application of the assigned drug. Subjects will be asked to apply the study drug 2 pumps 2 times a day to be applied topically on the affected area during a one week treatment period. Application instructions will be provided to the subjects. Prior to the first use, the study coordinator will prime the pump by pushing down fully 4 times, and to discard any solution to ensure an accurate dose is delivered during first use.

Study Drug Application at Home

Written study drug application instructions, storage instructions, and a study diary will be provided to all subjects at the time of discharge from the clinic.

At home, subjects will continue to apply the study drug twice a day. In the 1 week diary, subjects will record daily drug application, pain scores before and after application and any other oral pain medication taken. Subjects are permitted in the study to take acetaminophen (325 to 650 mg tablet up to 4 times a day) if pain persists even with the study drug application.

Subjects will be instructed to observe the following instructions:

1. Please wash and dry hands before and after use.
2. Do not apply to skin with open wounds, or blistered or inflamed areas of the skin.
3. Avoid contact with your eyes and mucous membranes.
4. Do not apply external heat.
5. Do not shower for at least 30 minutes after applying study drug.

6. Do not wear clothing over the treated area until the area is dry.
7. Do not take other NSAID (like aspirin, ibuprofen, naproxen, ketorolac, diclofenac, etc.) while enrolled on this study. Please contact the study doctor or research staff if you are unsure.
8. Keep the bottle away from direct sunlight.
9. Protect the treated area from natural or artificial sunlight.
10. Wait until the treated area is dry before applying sunscreen, insect repellent, lotion, moisturizer or cosmetics to the same area.
11. Avoid skin-to-skin contact between other people and the treated area until the treated area is completely dry.

Follow- Up

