All subjects will be asked to come back for a study visit at one week (+/- 1 day) after initial dosing for assessment, to return the completed diary and remainder of the study drug. If subjects are not able to physically return for the follow-up visit, a remote video follow-up visit can be done for the required study assessments. Remote visits will not be audio or video recorded. Subjects completing a remote video follow-up visit must return to clinic for a physical follow-up visit when able. Subjects who do not receive adequate pain relief during the study may opt to drop out and resume taking their prior prescribed medications or they may return to their primary care physician. If this occurs, subjects will be asked to discard any unused study drug.

DURATION OF STUDY:

This study will be for 1 weeks from initial study drug application.

OUTCOME MEASURES:

The following assessments would be determined:

1. Numerical Pain Rating Scale (NPRS) score at:
 - a. time of enrollment
 - b. 24-hours earlier
 - c. 1 week later twice daily (am and pm)
2. Time of Onset of Action of Bonipar measurement
3. Report of any adverse effects or complications.

Protected health information (PHI) will be kept confidential as required by law. Some information collected about this research study may be kept in a research study record separate from the medical record, and some research information may also be part of the medical record. Except when required by law, subject will not be identified by name, social security number, address, telephone number, or any other direct personal identifier in study records disclosed outside of Duke University Health System (DUHS). For records disclosed outside of DUHS, subject will be identified using a unique code number. The unique code and date of birth will be reported on the Case Report Forms (CRF). The key to the code will be kept in a locked file.

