If the patient is not eligible or does not want to participate in the study their PHI is shredded and destroyed. For consented patient, PHI is kept in research office in a locked desk or cabinet when not being used by the research staff. The information we review are on individual computers which are password protected. The office doors are kept locked when no one from the research staff is in the office. The only people who have access to the rooms are the research staffs which are listed on the key personnel sheet. Study records will be retained with Duke for at least six years after the study is completed.

Selection of Subjects

- List inclusion/exclusion criteria and how subjects will be identified.

INCLUSIONARY CRITERIA:

1. Subject with acute and chronic localized musculoskeletal pain
2. Ages 18 to 80 years
3. Female subjects of childbearing age* must have a negative pregnancy test

Female subjects of childbearing age who are sexually active must agree to use appropriate contraceptive measures for the duration of the study. Medically acceptable contraceptives include: (1) surgical

sterilization (such as tubal ligation or hysterectomy), (2) approved hormonal contraceptives (such as birth control pills, patches, implants or injections), (3) barrier methods (such as a condom or diaphragm) used with a spermicide, or (4) an intrauterine device (IUD).

4. Willing to provide written informed consent
5. Patients taking opioid or NSAID for their musculoskeletal pain may be included if pain is inadequately controlled

*A woman of childbearing age is post-menarche and premenopausal, physiologically capable of fertilization and pregnancy.

EXCLUSIONARY CRITERIA:

1. Use of any topical agents on the affected area within 3 days of screening
2. Subject with active skin lesions or active skin disease or with current cutaneous manifestations of systemic illnesses
3. Subject with known uncontrolled diabetes at time of screening (A1C of more than 9)
4. Subject with uncontrolled hypertension at time of screening (SBP > 160 and DBP > 95)
5. Subject with active uncontrolled GERD (defined as more than 2 episodes per week) or history of peptic ulcer disease
6. Subject with active cancer or active spinal cord lesions
7. Recent spine surgery (within 3 months of screening)
8. Subject with allergies to diclofenac or to other non-steroid anti-inflammatory drugs (NSAID)
9. Known allergies to any oils, methyl salicylate and/or camphor
10. Subject is pregnant or lactating

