- Describe and justify any costs that the subject will incur as a result of participation; ordinarily, subjects should not be expected to pay for research without receiving direct benefit.

There will be no additional costs as a result of being in this study. Bonipar and diclofenac topical solution 1.5% will be provided free of charge for use in this study.

Data Analysis & Statistical Considerations

- Describe endpoints and power calculations. Provide a detailed description of how study data will be analyzed, including statistical methods used, and how ineligible subjects will be handled and which subjects will be included for analysis. Include planned sample size justification. Provide estimated time to target accrual and accrual rate. Describe interim analysis including plans to stop accrual during monitoring. Phase I studies, include dose escalation schema and criteria for dose escalation with definition of MTD and DLT.

The primary objective of the study is to evaluate the reduction in acute and chronic musculoskeletal pain by Bonipar in comparison to conventional treatment of diclofenac topical solution 1.5%. Pain responses at base line and at two-week follow up will be measured in the scale of 0 to 10, where 0 indicates no pain and 10 indicates highest level of pain. For each patient, primary outcome variable will be measured in two ways: i) compute whether the decrease in pain by 50% between baseline and 1-week follow-up (i.e. binary variable) and, ii) calculate the absolute difference in pain score between baseline and 1-week follow-up (continuous variable). Statistical power and sample size was determined based on the binary outcome variable.

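### NSAID and opioid users may enrol, but the plan does not say when NSAIDs stop relative to the baseline pain score or what happens to opioids, so the 50% response can mix drug effect with NSAID withdrawal

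*Combined protocol and SAP*

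**What the plan says.** All references are to the combined protocol and SAP.

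- Selection of Subjects, inclusion criterion 5: "Patients taking opioid or NSAID for their musculoskeletal pain may be included if pain is inadequately controlled".
- Study Drug Application at Home, instruction 7: "Do not take other NSAID (like aspirin, ibuprofen, naproxen, ketorolac, diclofenac, etc.) while enrolled on this study".
- Follow-Up: patients without adequate relief "may opt to drop out and resume taking their prior prescribed medications".
- Exclusion criterion 1 sets the only pre-screening interval for an analgesic: "Use of any topical agents on the affected area within 3 days of screening". None is given for oral NSAIDs or opioids.
- Baseline Assessments collect "pain intensity 24 hours prior and immediately before study drug application".
- On study, "Subjects are permitted in the study to take acetaminophen", and the diary records "any other oral pain medication taken".
- Data Analysis & Statistical Considerations defines the binary primary outcome: "compute whether the decrease in pain by 50% between baseline and 1-week follow-up". Absolute change is the second form. The success rates are compared without adjustment. A linear regression of the change in pain score adjusts for confounders, with pain type and prior duration named as examples. Prior analgesic use is not named, and no analysis uses the diary record of oral analgesics.

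**The concern.** The primary endpoint is a within-patient ratio of two pain scores. It measures the study drug cleanly only if the rest of the patient's analgesia is comparable at both times. The plan admits NSAID users and then bars NSAIDs, but it does not place the stop before or after the baseline score. If baseline is scored on the NSAID, the 1-week score reflects the study drug minus the lost NSAID.

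Two consequences could follow. Success could become less likely in both arms, which can reduce power. If the loss is proportional, the arm difference also shrinks, and in a non-inferiority trial that makes it easier to pass a treatment that is truly worse. Sites may also handle the unstated points, especially opioids, in different ways.

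**Working it through.** **Inputs.** From the Power Calculation section: control success 52%, Bonipar 62%, margin 10 points, one-sided alpha 0.05, 76 per arm. The documents do not give the share f of patients who stop an NSAID, or the factor r by which stopping multiplies their chance of success. Both are assumptions here.

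**1. The plan's own figure.** n per arm = (1.645 + 0.842)² × [0.52×0.48 + 0.62×0.38] / (0.10 + 0.10)² = 6.183 × 0.4852 / 0.04 = 75.0. With pooled variance, 2×0.57×0.43 = 0.4902 gives 75.8, hence 76. The stated 76 is reproduced. Power at 76 (unpooled): SE = √(0.4852/76) = 0.0799, and Φ(0.20/0.0799 − 1.645) = 80.5%.

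**2. One patient (assumed scores).** A patient at 5 on an NSAID must reach 2.5 to count as a success. If the unmedicated level is 6, that is a fall of 1 − 2.5/6 = 58% from that level; if it is 7, 1 − 2.5/7 = 64%. The criterion is then stricter than 50% for this patient.

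**3. Proportional loss in both arms.** Every success rate is multiplied by k = 1 − f + f·r. P(declare non-inferiority) = Φ((0.10 + difference)/SE − 1.645), unpooled, 76 per arm. The error column takes Bonipar as truly 10 points worse (52% v 42%) when background medication is unchanged. The power column uses 52% v 62%.

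Example with f = 30%, r = 0.5: k = 0.85.
- Error: 44.2% v 35.7%, SE = √[(0.442×0.558 + 0.357×0.643)/76] = 0.0792, Φ(0.015/0.0792 − 1.645) = 7.3%.
- Power: 44.2% v 52.7%, SE = 0.0808, Φ(0.185/0.0808 − 1.645) = 74.1%.

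| f | r | k | Control rate | True −10 appears as | False non-inferiority | Power |
|---|---|---|---|---|---|---|
| 10% | 0.9 | 0.990 | 51.5% | −9.9 | 5.1% | 80.0% |
| 10% | 0.75 | 0.975 | 50.7% | −9.75 | 5.3% | 79.3% |
| 10% | 0.5 | 0.950 | 49.4% | −9.5 | 5.7% | 78.2% |
| 30% | 0.9 | 0.970 | 50.4% | −9.7 | 5.4% | 79.1% |
| 30% | 0.75 | 0.925 | 48.1% | −9.25 | 6.0% | 77.1% |
| 30% | 0.5 | 0.850 | 44.2% | −8.5 | 7.3% | 74.1% |
| 50% | 0.9 | 0.950 | 49.4% | −9.5 | 5.7% | 78.2% |
| 50% | 0.75 | 0.875 | 45.5% | −8.75 | 6.8% | 75.0% |
| 50% | 0.5 | 0.750 | 39.0% | −7.5 | 9.3% | 70.6% |

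**4. Equal absolute loss in both arms.** Both rates fall by the same number of points, so a true −10 stays −10 and the error rate is Φ(0 − 1.645) = 5.0%. If 30% of patients each lose 26 points, both rates fall by 0.30×26 = 7.8 points. Power at 44.2% v 54.2% is then 79.8%, almost unchanged.

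**The case against.** Admitting patients whose NSAID is not working and replacing it with study drug is a coherent switch design, so criterion 5 and instruction 7 do not strictly contradict each other. Returning to earlier prescriptions after dropout fits stopped prescription NSAIDs and need not mean that opioids were stopped. The regression's covariate list is open-ended, and the diary captures oral analgesics. Because these patients were inadequately controlled on their NSAID, halving their chance of success may be too severe.

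All of this stands. It does not settle when the NSAID stops relative to baseline, or what happens to opioids. The regression concerns the pain-score change, so even an added covariate leaves the success-rate comparison untouched.

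A reader might infer four stronger claims that the documents do not support:

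- *Background medication differs between the two scores for all prior users.* For NSAID users the text allows this but does not fix the timing. For opioid users the plan is silent, and unchanged use is equally consistent with it.
- *Chance imbalance in prior use biases the comparison.* Allocation is randomised 1:1, so chance imbalance is random error, which the confidence interval already reflects.
- *Withdrawal always favours non-inferiority.* It does so under a proportional loss, but not under an equal absolute loss.
- *The 52% control rate cannot hold.* The cited source range is 39% to 92%, and even the most severe row of the table gives 39.0%.

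**Conclusion.** The point holds in a limited form. As written, an NSAID user's baseline can be scored on the NSAID and the 1-week score off it, which distorts the 50%-fall endpoint in those patients. Opioid treatment is uncontrolled. There is no systematic bias between arms from prior use itself, because randomisation balances it on average.

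The size cannot be fixed from the documents. Over the assumed grid, the false non-inferiority rate runs from barely above nominal (5.1%) to nearly double (9.3%), and power from 80.0% down to 70.6%. The upper end needs half the patients to be NSAID users and a halved chance of success. The inflation disappears if the loss is equal in absolute terms. The error rates are also relative to the arm difference under unchanged background medication, a target the plan does not spell out. This should be corrected, but the working gives no ground for a new sample size.

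**What to change.** Reconcile criterion 5, instruction 7 and the Follow-Up text: state what happens to NSAIDs and to opioids in use at screening, and when this occurs relative to the baseline NPRS. The clinical rule is for the investigator to choose.

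Whatever the rule, prespecify the following:

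1. Record prior NSAID use and prior opioid use (each yes/no) at baseline, from the medical-history review already planned.
2. Add both as covariates in the linear regression of pain-score change.
3. Estimate the success-rate difference and its 90% confidence interval stratified by prior NSAID use, for example as a Mantel-Haenszel risk difference. This brings prior use into the comparison on which non-inferiority rests. It accounts for chance imbalance and shows each stratum, but does not by itself undo dilution.
4. Repeat the comparison in patients not taking an NSAID at entry, as a supportive sensitivity analysis.

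The cost is protocol wording, two baseline items and slightly more analysis work, with no new visit. The non-user subset will be imprecise. With 30% users about 53 per arm remain (76×0.7), and power at 52% v 62% is Φ(0.20/√(0.4852/53) − 1.645) = 67%. With 50% users, 38 per arm remain and the same formula gives 55%. That analysis can support the main result but cannot carry the conclusion alone.

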***Please enter the Short Title you would like to use to reference the study:**

Bonipar for Acute & Chronic Muskuloskeletal Pain

* This field allows you to enter an abbreviated version of the Study Title to quickly identify this study.

Research Summary**State your primary study objectives**

The objective of this study is evaluate the efficacy and onset of action of Bonipar, a topical analgesic derived from a variety of essential oils, in controlling pain in patients with acute and chronic musculoskeletal pain, as compared to the topical NSAID, diclofenac topical solution 1.5%.

State your secondary study objectives

none

Please select your research summary form:

Standard Research Summary Template

This is the regular (generic) research summary template which is required for all regular applications (unless your protocol fits under the other research summary templates in this category). Use of these instructions is helpful for ensuring that the research summary contains all necessary elements.

Standard Research Summary**Purpose of the Study**

- Objectives & hypotheses to be tested

To evaluate the efficacy and onset of action of Bonipar in controlling pain in patients with acute and chronic musculoskeletal pain syndromes.

Background & Significance

- Should support the scientific aims of the research

Acute and chronic pain patients with musculoskeletal-skeletal pain are treated in many ways. The use of pharmacological agents in treating these is frequently associated with unacceptable complications: non-selective nonsteroidal anti-inflammatory drug (NSAID) may cause serious gastrointestinal disorders including hemorrhage requiring hospitalization and sometimes death; COX2-selective NSAIDS may also cause GI complications but more especially may cause coronary events especially in hypertensive patients; acetaminophen and related drugs may cause hepatic dysfunction and occasionally liver failure and opioids are usually associated with drug misuse, drug abuse, drug diversion and addiction which are currently assuming epidemic proportions in the USA. As a consequence of these undesirable pharmacological issues, the search for safe and effective drugs to treat both acute and chronic musculoskeletal pain continues.

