Topical analgesic have a place in managing musculoskeletal pain but their scientific efficacy has usually been anecdotal and seldom subjected to investigational scrutiny. These topical agents are relatively safe but may still have adverse effects by virtue of their pharmacological compositions. The use of natural compounds e.g. essential oils from selective herbal extracts have been used by many persons from tropical and subtropical regions for medicinal purposes including pain.

Thus, the objective of this study is to evaluate the efficacy and onset of action of Bonipar, a topical analgesic derived from a variety of essential oils, in controlling pain in patients with acute and chronic musculoskeletal pain, as compared to the topical NSAID, Diclofenac topical solution 1.5%.

Design & Procedures

- Describe the study, providing detail regarding the study intervention (drug, device, physical procedures, manipulation of the subject or the subject's environment, etc.). Discuss justifications for placebo control, discontinuation or delay of standard therapies, and washout periods if applicable. Identify procedures, tests and interventions performed exclusively for research purposes or more frequently than standard of care. Include alternative therapies, concurrent therapies discontinued per protocol, risk benefit ratio, and use of tissue/specimens. Discuss monitoring during washout periods if applicable. Include brief description of follow-up, if any.

This study is a non-inferiority study comparing efficacy and onset of action between the herbal extracts topical solution, Bonipar, and diclofenac sodium topical solution, diclofenac topical solution 1.5% (approved by the FDA as a topical analgesic). Approximately 240 Duke patients will be recruited from Duke Pain Clinic, and selected Duke primary care practices, as well as the Durham VA site. Individuals who report acute (less than 3 months duration) or chronic musculoskeletal pain of any intensity will be considered for enrollment into the study. After obtaining consent, eligible subjects will be will be randomized to receive Bonipar or diclofenac topical solution 1.5%.

For study purposes, diclofenac topical solution 1.5% will be used off-label—that is, it may be used for pain not known to be caused by osteoarthritis. However, this study does not aim to identify a new indication for diclofenac topical solution 1.5%.

Baseline Assessments

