11. Subjects who, within the past 3 months, have history of heart attack, stroke, or blood clot
12. Recent coronary artery bypass graft surgery (CABG) (i.e., within 6 months of screening)
13. Subject with history of alcohol or drug abuse within the past 3 months
14. Subject with history of severe liver or kidney disease or any other medical condition within 3 months of screening that may interfere with the subject's ability to participate in the study as determined by the Investigator

Subject Recruitment and Compensation

- Describe recruitment procedures, including who will introduce the study to potential subjects. Describe how you will ensure that subject selection is equitable and all relevant demographic groups have access to study participation (per 45 CFR 46.111(a) (3)). Include information about approximately how many DUHS subjects will be recruited. If subjects are to be compensated, provide specific prorated amounts to be provided for expenses such as travel and/or lost wages, and/or for inducement to participate.

To screen for eligible patients, a request for Waiver or Alteration of Consent and HIPAA Authorization will be obtained prior to start of study. An advertisement flyer and advertisement will be used. MyChart messages to subjects will be used, facilitated by DOCR. We gather screening information by reviewing MD appointments, medical history and clinical diagnosis from Epic Maestro Care, from Duke clinician referrals, and/or utilizing the phone script.

Patient's research opt-out status will be noted prior to approach. If patient expresses the would like to opt-out of all research contact, the PI or designee will complete the REDCap Survey (<https://redcap.duke.edu/redcap/surveys/?s=9NX7DY7DXX>) to convey the patient's information to the appropriate Maestro Care Analyst team and refer the patient to the Notice of Privacy Practices (<https://www.dukehealth.org/privacy>).

If the opt-out status is not present and the subject expresses interest in learning more about the study, the PI or designee will commence in approaching subject.

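### The hypertension exclusion joins its two blood-pressure limits with *and*, so a patient above only one of them stays eligible; it should read *or*.

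*Combined protocol and SAP*

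**What the plan says.** The rule appears twice in the combined protocol and SAP. In Selection of Subjects, exclusion criterion 4 is "Subject with uncontrolled hypertension at time of screening (SBP > 160 and DBP > 95" (closing bracket follows). In Design & Procedures, under Baseline Assessments, it is "We will exclude patients with SBP > 160 and DBP > 95 at screening". The thresholds and the connector are the same in both, so the two statements do not contradict each other.

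Four other places bear on how the word should be read or on what else might cover the gap:

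- Inclusion criterion 1 asks for "Subject with acute and chronic localized musculoskeletal pain", while Design & Procedures gives the same entry rule as "Individuals who report acute (less than 3 months duration) or chronic musculoskeletal pain of any intensity".
- Exclusion criterion 9 is "Known allergies to any oils, methyl salicylate and/or camphor".
- Exclusion criterion 14 lets the investigator exclude for "any other medical condition within 3 months of screening that may interfere with" participation. It names no blood-pressure value.
- Exclusion criteria 11 and 12 cover recent heart attack, stroke, blood clot and bypass surgery, not blood pressure.

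**The concern.** A criterion labelled as uncontrolled hypertension should exclude a patient whose systolic or diastolic pressure is clearly out of control. Joined by *and*, it excludes only patients who exceed both limits. A systolic pressure of any height is then acceptable if the diastolic is 95 or below, and a diastolic pressure of any height is acceptable if the systolic is 160 or below. That defeats the label.

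What is at stake is eligibility and patient safety, not inference. One arm receives an NSAID, and screening is the only point at which the protocol describes a blood-pressure measurement. The Follow-Up section lists none and allows a video visit, and Data & Safety Monitoring plans no monitoring board. Recruitment runs across a pain clinic, primary care practices and a VA site, so the threshold needs one meaning for every screener.

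**Working it through.** No figure in the plan depends on this rule, so there is nothing to reproduce. The check is a logical reading of the criterion and a search for any other rule that closes the gap.

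**Inputs.** Systolic limit 160 and diastolic limit 95, from exclusion criterion 4 and Baseline Assessments. The patient readings below are illustrative and are not from the documents.

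**The two rules.** Write S for systolic and D for diastolic pressure.

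- As written: exclude if S > 160 *and* D > 95. Equivalently, keep if S ≤ 160 *or* D ≤ 95.
- As proposed: exclude if S > 160 *or* D > 95. Equivalently, keep only if S ≤ 160 *and* D ≤ 95.

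| Combination | Example | S > 160 | D > 95 | Under *and* | Under *or* |
|---|---|---|---|---|---|
| Systolic only | 190/90 | yes | no | eligible | excluded |
| Diastolic only | 150/110 | no | yes | eligible | excluded |
| Both | 165/100 | yes | yes | excluded | excluded |
| Neither | 150/90 | no | no | eligible | eligible |

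*And* excludes 1 of the 4 combinations and *or* excludes 3. The difference, 3 − 1 = 2, is the two single-limit rows. These are counts of logical cases, not shares of patients.

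**Does anything else close the gap?** No. Criterion 14 is investigator judgement without a limit. Criteria 11 and 12 concern recent events and surgery. No part of the document says that exceeding one limit is enough.

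**How would a screener read the word?** The document points both ways.

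- *Loose use.* Inclusion criterion 1 joins acute and chronic pain with *and*, where Design & Procedures uses *or*. No screener would demand that a patient have both. This supports *or* as the intended meaning in criterion 4.
- *Careful use.* In the exclusion list itself, criteria 2, 5, 6, 8, 10, 11, 13 and 14 use *or* where either item suffices, and criterion 9 uses *and/or*. Against that pattern, *and* in criterion 4 naturally reads as requiring both.

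Two screeners could therefore classify the same patient differently, and the one who follows the words admits the patient.

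**The case against.** The strongest reply is that the text is ambiguous, not wrong. The Baseline Assessments sentence has a plural noun and can be read as naming two groups of patients, those above the systolic limit and those above the diastolic limit. On that reading 190/90 and 150/110 are already excluded. No part of the document states *or*, so a deliberately permissive rule for a short topical study cannot be ruled out. It can also be said that the argument treats *and* as loose to establish intent and as strict to establish harm.

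Part of this stands. The intended wording is an inference. But the two-groups reading already means *or*, so the correction would only make it explicit. It also does not fit criterion 4, where the subject is singular and the bracket works as a definition. The argument does not need *and* to be both loose and strict: the loose use elsewhere is evidence of what was meant, and the strict reading is what the exclusion list tells a screener to apply. If *and* was intended, the protocol should say so and justify it.

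The reply on severity stands in full. Dosing is two pumps twice daily for one week. Baseline Assessments accompanies its pregnancy exclusion with "Although the risk of serious side effects is low when diclofenac is applied to the skin". Recent cardiovascular events and bypass surgery are excluded separately, and the home instructions forbid other NSAIDs, so a patient who enters on an oral NSAID stops it. The Background remark that a drug class "may cause coronary events especially in hypertensive patients" concerns COX2-selective NSAIDs. It shows that the sponsor has hypertension in mind but is not evidence about topical diclofenac.

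**Conclusion.** The concern holds. In both places where the rule is stated, the wording excludes only patients above both limits, and nothing else in the protocol sets a blood-pressure threshold. The gap is exactly the patients above one limit and not the other. Its size in patients cannot be computed without a blood-pressure distribution, which the documents do not give.

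The conclusion assumes that *or* was intended. That rests on the criterion's own label, on a separate limit having been set for each pressure, and on the loose use of *and* in inclusion criterion 1; confidence in it is medium. The change should be made, but severity is low. Because the rule acts before randomisation and equally on both arms, the sample sizes (152, 168 and 240), the power, the significance level and the planned analyses are unaffected.

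**What to change.** Replace *and* with *or* between the two limits in both places, so that each condition reads SBP > 160 or DBP > 95:

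- Selection of Subjects, exclusion criterion 4.
- Design & Procedures, Baseline Assessments, the blood-pressure item.

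Both must change together, or the document will contradict itself. The cost is one word in each place and possibly a few more screen failures.
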